4 STUDY DESIGN

This is a prospective, multi-center, phase II study of up to 25 patients to evaluate the efficacy of the EGFR inhibitor, cetuximab in patients with mCRC harboring APC, TP53 and RAS mutations. The study will be conducted at Intermountain Healthcare and Huntsman Cancer Institute at the University of Utah, Salt Lake City, Utah.

4.1 Study Duration

The estimated duration of the study from start of screening to last participant completed the study and duration of participation is approximately 24 months

4.2 End of Study

A subject is considered to have completed the study if he or she has completed all phases of the study including the last visit or the last scheduled procedure shown in the Schedule of Events.

The study will end when the last subject completes the last visit or last contact, discontinues from the study, or is lost to follow-up, whichever occurs first. In addition, the sponsor may terminate the study at any time. If at any time, the sponsor terminates the study any subjects receiving clinical benefit from the study intervention may roll over to an expanded access protocol to ensure continued access to the study medication.

5 STUDY POPULATION

Potential study participants must meet all inclusion criteria and no exclusion criteria to be deemed eligible for trial participation. To ensure subject safety, all subjects must be deemed eligible at the time of study registration and must continue to meet eligibility criteria up to cycle one day one dosing. This eligibility checklist is used to determine subject eligibility and will be filed with the enrolling investigator's signature in the subject research chart.

5.1 Inclusion Criteria

1. Male or female subject aged ≥ 18 years.
2. Histologically confirmed metastatic colorectal adenocarcinoma with mutant APC, TP53 and RAS genes as determined by the local CLIA-certified laboratory are eligible. All RAS mutations are allowed (KRAS, NRAS, HRAS). Patients with wild type RAS, APC or TP53 are ineligible.
3. Progression or unwanted toxicities on at least 2 prior lines of treatment including 5-Flourouracil, oxaliplatin and irinotecan based regimen
4. Study participants must have measurable disease by RECIST 1.1 criteria by CT or MRI.
5. ECOG Performance Status ≤ 2 .
6. Study participants with treated and/or stable brain metastases are allowed
7. Study participants must have anticipated life expectancy > 3 months
8. Adequate organ function as defined as:
 - Hematologic:
 - Absolute neutrophil count (ANC) $\geq 1000/\mu\text{L}$
 - Platelet count $\geq 100,000/\text{mm}^3$
 - Hemoglobin $\geq 9 \text{ g/dL}$
 - Hepatic:
 - Serum Bilirubin $\leq 2 \times \text{ULN}$ or $\leq 3 \times \text{ULN}$ for subjects with Gilbert's syndrome.
 - Aspartate transaminase (AST) and alanine transaminase (ALT) ≤ 3.0 times the upper limit of normal (ULN; or 5.0 times the ULN in the setting of liver metastases)

- Renal:
 - Serum creatinine \leq 1.5 times the ULN, or creatinine clearance (measured via 24-hour urine collection) \geq 40 mL/minute (that is, if serum creatinine is $>$ 1.5 times the ULN, a 24-hour urine collection to calculate creatinine clearance must be performed)
- 9. _____ For female subjects: Because the teratogenicity of cetuximab is not known, the patient, if sexually active must have a negative serum pregnancy test or surgically sterile or using effective contraception (hormonal or barrier methods) or evidence of post-menopausal status. The post-menopausal status will be defined as having been amenorrheic for 12 months without an alternative medical cause. The following age-specific requirements apply:
 - Women $<$ 50 years of age:
 - Amenorrheic for \geq 12 months following cessation of exogenous hormonal treatments; and
 - Luteinizing hormone and follicle-stimulating hormone levels in the post-menopausal range for the institution; or
 - Underwent surgical sterilization (bilateral oophorectomy or hysterectomy).
 - Women \geq 50 years of age:
 - Amenorrheic for 12 months or more following cessation of all exogenous hormonal treatments; or
 - Had radiation-induced menopause with last menses $>$ 1 year ago; or
 - Had chemotherapy-induced menopause with last menses $>$ 1 year ago; or
 - Underwent surgical sterilization (bilateral oophorectomy, bilateral salpingectomy, or hysterectomy).
- 10. _____ Female subjects of childbearing potential must have a negative pregnancy test within 7 days prior to enrollment and male subjects with a sexual partner of childbearing potential must agree to use a highly effective method of contraception throughout the study and for at least 2 months after last study treatment administration.
- 11. _____ Male subjects must agree to use a condom during intercourse for the duration of study therapy and for at least 2 months after last study treatment administration.
- 12. _____ Recovery to baseline or \leq Grade 1 CTCAE v5.0 from toxicities related to any prior cancer therapy, unless considered clinically not significant by the treating investigator.
- 13. _____ Able to provide informed consent and willing to sign an approved consent form that conforms to federal and institutional guidelines.

5.2 Exclusion Criteria

1. _____ Prior use of systemic anti-EGFR therapy including cetuximab or panitumumab is not allowed but prior use irinotecan, oxaliplatin, regorafenib or TAS-102 is allowed

2. _____ Study participants with prior or concurrent malignancy whose natural history or treatment have the potential to interfere with the safety or efficacy assessment of the investigational regimen, as determined by the investigator

3. _____ Study participants with new or progressive brain metastases (active brain metastases) or leptomeningeal disease who need immediate CNS specific treatment during first cycle of treatment as determined by the treating physician.

Note: Brain metastases or cranial epidural disease adequately treated with radiotherapy and/or surgery and stable for at least 4 weeks before the first dose of study treatment will be allowed on trial. Subjects must be neurologically asymptomatic and without corticosteroid treatment at the time of the first dose of study treatment.

4. _____ Current evidence of uncontrolled, significant intercurrent illness including, but not limited to, the following conditions:

- The patient has clinically relevant coronary artery disease or history of myocardial infarction in the last 12 months or high risk of uncontrolled arrhythmia or uncontrolled cardiac insufficiency.
- The patient has uncontrolled or poorly-controlled hypertension (>180 mmHg systolic or > 130 mmHg diastolic).
- Any other condition that would, in the Investigator's judgment, contraindicate the subject's participation in the clinical study due to safety concerns or compliance with clinical study procedures (e.g., infection/inflammation, intestinal obstruction, unable to swallow medication, [subjects may not receive the drug through a feeding tube], social/ psychological issues, etc.)

5. _____ Known HIV infection with a detectable viral load within 6 months of the anticipated start of treatment.

Note: Subjects on effective antiretroviral therapy with an undetectable viral load within 6 months of the anticipated start of treatment are eligible for this trial.

6. _____ Active infection including tuberculosis (clinical evaluation that includes clinical history, physical examination, radiographic findings, and TB testing in line with local practice), hepatitis B (known positive HBV surface antigen (HBsAg) result), or hepatitis C.

Note: Subjects with a past or resolved HBV infection (defined as the presence of hepatitis B core antibody [anti-HBc] and absence of HBsAg) are eligible. Subjects positive for hepatitis C (HCV) antibody are eligible only if polymerase chain reaction is negative for HCV RNA.

7. _____ Medical, psychiatric, cognitive, or other conditions that may compromise the subject's ability to understand the subject information, give informed consent, comply with the study protocol or complete the study.

8. Known prior severe hypersensitivity attributed to compounds of chemical or biologic composition similar to those of cetuximab, or if the patient had red meat allergy/tick bite history (NCI CTCAE v5.0 Grade ≥ 3).
9. Live attenuated and inactive vaccinations within 4 weeks of the first dose of study treatment and while on trial is prohibited. COVID-19 vaccines are allowed
10. The patient is pregnant or breast-feeding.

I certify that this patient meets all inclusion and exclusion criteria for enrollment onto this study.

Investigator Signature

Date

Time

5.3 Registration

Subjects must meet all of the eligibility requirements before registration. Study-related screening procedures can only begin once the subject has signed the consent form. Subjects must not begin protocol treatment prior to registration.

Treatment should start as soon as logistically possible after registration.

To register eligible subjects on study, complete a Clinical Trials Office Subject Registration Form and submit to [contact].

For sites outside of Huntsman Cancer Institute, submit registration forms to [contact]

5.4 Contraception

Due to the known abortifacient and teratogenic effects of Cetuximab, a form of highly effective contraception is required for the duration of study therapy. Female subjects of childbearing potential must use a form of highly effective contraception from the start of study therapy until 2 months after the last dose of study therapy. Male subjects with a partner of childbearing potential must agree to use a method of highly effective contraception from the start of study therapy until 2 months after the last dose of study therapy.

Acceptable highly effective contraceptive methods include:

- Bilateral tubal occlusion
- Vasectomized partner
- Intra-uterine devise (IUD) or hormone-releasing system (IUS)
- Any hormonal (estrogen combined with progesterone or progesterone alone) contraception associated with inhibition of ovulation: implanted, oral, intravaginal, transdermal, or injectable.

- Spermicide with a compatible barrier method (i.e. diaphragm, sponge, or male or female condoms).
- Abstinence from heterosexual intercourse.

Due to concern for drug transfer through seminal fluid, male subjects must agree to use a condom during heterosexual and homosexual intercourse from the start of study therapy until 2 months after the last dose of study therapy.

5.5 Screen Failures

Screen failures are defined as participants who consent to participate in the clinical trial but do not meet subject eligibility criteria. These subjects will not be entered into the study or begin study intervention. However, minimal information is required to ensure transparent reporting of screen failure participants to meet the Consolidated Standards of Reporting Trials (CONSORT) publishing requirements. Minimal information includes, but may not be limited to, demography, screen failure details, eligibility criteria, and any serious adverse event (SAE) experienced during screening, but prior to being deemed ineligible.

Individuals who do not meet the criteria for participation in this trial (screen failure) may be rescreened at the Investigator's discretion.

5.6 Strategies for Recruitment

Investigators will identify potential subjects in the setting of their outpatient clinics, in tumor boards and referrals from other medical oncologists. All potentially eligible patients irrespective of their age, gender, and race will be screened. This study will be posted on clinicaltrials.gov.

5.6.1 Number of Subjects

Up to 25 patients to get 21 evaluable patients for efficacy as defined in Section 9.2.2.

5.6.2 Number of Study Sites

This is a multi-center study conducted at Intermountain Healthcare and Huntsman Cancer Institute.

6 STUDY INTERVENTION

6.1 Administration Schedule

The treatment plan includes single agent cetuximab. Cetuximab will be administered every 2 weeks (14 days). The initial dose of 500 mg/m² is to be administered by IV infusion over 120 minutes. Each cycle will be defined as 14 days of treatment.

Sites should make every effort to target infusion timing to be as close to 120 minutes as possible. However, given the variability of infusion pumps from site to site, a window of -5 minutes and +10 minutes is permitted (i.e., infusion time is 120 minutes: -5 min / +10 min).

In an effort to prevent a hypersensitivity reaction, all patients should be premedicated with

diphenhydramine hydrochloride 50 mg (or an equivalent antihistamine) by IV given approximately 30-60 minutes prior to the first dose of cetuximab. Premedication may be administered prior to subsequent doses, but at the Investigator's discretion, the dose of diphenhydramine (or a similar agent) may be reduced.

Patients should be closely monitored for treatment-related adverse events, especially hypersensitivity reactions, during the infusion and the post-infusion observation hour. For the duration that patients are on protocol therapy, adverse event monitoring will be done continuously. Patients will be evaluated for adverse events at each visit and are to be instructed to call their physician to report any clinically significant adverse events between visits.

6.2 Cetuximab

6.2.1 Investigational Product Supplies

The Investigational Drug Services Pharmacy at Huntsman Cancer Institute and Intermountain Healthcare Principal Investigator will ensure appropriately trained and delegated personnel will receive, inventory, and stored all investigational products per applicable laws and regulations.

6.2.2 Preparation and Dispensing

The investigator or qualified personnel who are familiar with procedures that minimize undue exposure to themselves and to the environment will prepare, handle and dispense all investigational supplies. Appropriate records will be kept to accurately show all dispensing activates and Investigational Product (IP) will be supplied only to subjects deemed eligible for study therapy. IP may not be dispensed to subjects who have not been enrolled in the trial.

Drug preparation: The calculated amount of cetuximab should be withdrawn from the appropriate number of vials and injected into an empty sterile container (glass, PVC or non-PVC plastic) for IV infusion. Cetuximab should not be mixed with other drugs or diluted with infusion solutions. Do not shake. Cetuximab should be administered through a 0.22 micrometer in-line filter. The solution should be clear and colorless and may contain a small amount of easily visible white amorphous cetuximab particulates. DO NOT SHAKE OR DILUTE. Cetuximab can be administered via infusion pump or syringe pump but must not be administered as an IV push or bolus. Cetuximab should be piggybacked to the patient's infusion line. Prime the infusion line with cetuximab before starting the infusion. Use 0.9% saline solution to flush the line at the end of the infusion. In this study cetuximab will be administered at dose 500 mg/m² as an IV infusion over 120 minutes the initial dose followed by 120 minutes subsequent doses.

Drug dosing guidelines: The total administered dose of chemotherapy may be rounded up or down within a range of 5% of the actual calculated dose. It is not necessary to change the dose of chemotherapy or cetuximab administered unless the calculated dose changes by $\geq 10\%$.

Drug Disposal: The unused portions of injectable chemotherapeutic agents supplied as single-dose preparations will be discarded within eight hours of vial entry to minimize the risk of bacterial contamination.

6.2.3 Accountability and Compliance

Subject compliance with the treatment and protocol includes willingness to comply with all aspects of the protocol. At the discretion of the principal investigator, a subject may be discontinued from the trial for non-compliance with follow-up visits or study drug.

Information pertaining to study drug compliance (i.e., date time, and dose) will be recorded in the corresponding electronic case report form (eCRF) by the study team.

Any reason for non-compliance will be documented in the subject's research chart and the corresponding eCRF. At the discretion of the principal investigator, a subject may be discontinued from the trial for non-compliance with study visits or study drug.

All doses of Cetuximab will be administered at the investigational site by qualified medical staff. The start and stop times of the infusion, along with the total volume administered, will be recorded in the subjects' medical records. Additionally, the start and stop times of any interruptions to infusions and/or changes in the rate of infusion will be recorded in the subject's medical records. Any reasons that a dose other than the protocol-specified dose, rate, or dosing schedule was administered should be documented in the subject's research chart.

Depending on the patient's BSA, 7-9 vials for bi-weekly doses will be needed. A suggested initial shipment is 20 vials. Will allow 5-7 business days for shipment of drug from receipt of the request.

All products will be shipped via Federal Express in a temperature-controlled container. Shipments will be made on Monday through Thursday for delivery Tuesday through Friday. There will be no weekend, holiday or Monday delivery of drugs. The cetuximab supplies are study-specific but not patient-specific. Cetuximab ordered may be used for multiple patients on this study.

Inside each shipping container, a disposable electronic unit (TagAlert) to ensure the product has remained at the appropriate temperature during shipping may be included. This unit may be attached to an information card. The LCD display will show "OK" (indicating no alarm has been triggered) or a black bar and the number(s) 1-4 (indicating an alarm/alarms have been triggered).

6.3 Dose Interruptions

Dose interruptions for study treatment-related AEs are allowed as per the dose modification recommendations (Section 6.5). Doses of Cetuximab that were not administered due to toxicity will not be replaced within the same cycle. In addition to dose interruption, the need for a dose reduction at the time of treatment resumption should also be considered based on the dose modifications recommendations. If a toxicity-related dose delay lasts for > 28 days, treatment will be discontinued permanently and the subject should be removed from study treatment. If a subject requires a dose hold for > 28 days for a non-treatment related adverse event or situation (i.e. radiation therapy) the subject may continue on study only after approval and discussion with the Principal Investigator and Medical Monitor.

6.4 Dose Reductions

Following dosing interruption due to treatment-related toxicity, the study drug may need to be resumed at a reduced dose as per the dose modification recommendations. Dose reduction should proceed by decreasing the administered dose by one dose level per Table 1.

Once the study treatment has been reduced for a given patient, all subsequent cycles will be administered at that dose level. Intra-patient dose re-escalation is not allowed except as described in the toxicity management guidelines, Section 6.5

Table 1: Cetuximab Reduction Levels

Dose Level	Cetuximab
Dose Level 0	500 mg/m ²
Dose Level -1	400 mg/m ²
Dose Level -2	300 mg/m ²
Dose Level -3	250 mg/m ²

6.5 Dose Modifications Guidelines

Subjects experiencing adverse events attributed to study drug may undergo dose modifications for toxicity management. Dose modification guidelines are provided below for adverse events considered to be related to study medication. If either medication requires reduction below Dose Level -3 for toxicity management, study therapy will be discontinued. This study will utilize the CTCAE (NCI Common Terminology Criteria for Adverse Events) Version 5.0 for adverse event and serious adverse event reporting.

Hematological toxicities:

- No cetuximab dose modifications will be made for hematologic toxicity.

Gastrointestinal toxicities:

- No cetuximab dose modifications will be made for diarrhea, mucositis, nausea, or vomiting.

Pulmonary Toxicity

- For grade 2 or worsening pulmonary symptoms unrelated to underlying cancer, cetuximab therapy should be stopped and symptoms investigated. Cetuximab therapy may resume when symptoms resolve to \leq grade 1.
- For \geq grade 3 cough, dyspnea, hypoxia, pneumonitis, or pulmonary infiltrates, skip cetuximab until interstitial lung disease is ruled out. Discontinue all protocol therapy if interstitial lung disease is confirmed.

Hypomagnesemia

- Hypomagnesemia has been seen with cetuximab. Should hypomagnesemia occur, magnesium supplementation should be provided. No dose adjustment is required; however, continue careful monitoring.

Cutaneous Toxicity

- Acne is the most common cutaneous toxicity noted with cetuximab. While there is no clear evidence of benefit, over-the-counter or prescription acne medications designed to treat the acne-like rash may be used for patients who experience the acne-like rash associated with EGFR inhibitors. The investigator could also consider concomitant treatment with topical and/or oral antibiotics; topical corticosteroids are not recommended

Table 2: Cetuximab Dose Delays Due to Cutaneous Toxicity

	Cetuximab	Outcome	Cetuximab dose modification
Grade 3 Rash			
1 st occurrence	Skip infusion 1-2 weeks	If improvement	Continue 500mg/m ²
		If no improvement	Discontinue cetuximab
2 nd occurrence	Skip infusion 1-2 weeks	If improvement	Reduce to 400mg/m ²
		If no improvement	Discontinue cetuximab
3 rd occurrence	Skip infusion 1-2 weeks	If improvement	Reduce to 300mg/m ²
		If no improvement	Discontinue cetuximab
4 th occurrence	Skip infusion 1-2 weeks	If improvement	Reduce to 250 mg/m ²
		If no improvement	Discontinue cetuximab
5 th occurrence	Discontinue cetuximab		
Grade 4 Rash			
	Discontinue cetuximab		

There will be no dose level reductions below a biweekly dose of 250 mg/m² for cetuximab. Cetuximab dose reductions are permanent, that is, there will not be any re-escalation of dose. Discontinue cetuximab if doses are skipped for more than 4 consecutive weeks.

Nail disorders

- For grade 3 nail disorders, cetuximab may be skipped for up to 3 weeks and if no improvement, reduce dose to 400 mg/m² for 1st occurrence, 300 mg/m² for 2nd

occurrence, 250 mg/m² for 3rd occurrence and discontinue cetuximab if there is no improvement after 3 weeks.

Hypersensitivity and infusion reactions

- Note that the NCI CTCAE defines these reactions differently: “Cytokine release syndromes/acute infusion reactions are different from allergic/hypersensitivity reactions, although some of the manifestations are common to both AEs. An acute infusion reaction may occur with an agent that causes cytokine release (e.g., monoclonal antibodies or other biological agents). Signs and symptoms usually develop during or shortly after drug infusion and generally resolve completely within 24 hours of completion of infusion.” See the “Syndromes” section of the CTCAE version 5.0 for a complete list of signs and symptoms of “Cytokine release syndrome/acute infusion reaction;” and see the “Allergy/Immunology” section for a description of hypersensitivity.
- Dose modifications for hypersensitivity reactions to Cetuximab:
 - For grade 1 hypersensitivity reactions (transient rash, drug fever < 38°C): Decrease the infusion rate by 50% until symptoms resolve, then resume at the initial planned rate.
 - For grade 2 hypersensitivity reactions (urticaria, drug fever ≥ 38°C and/or asymptomatic bronchospasm): Stop infusion. Administer H1 and/or H2 blockers, and/or steroids according to institutional policy. Restart the infusion when symptoms resolve and pretreat before all subsequent doses. Treat according to institutional policy.
 - For grade 3 or grade 4 hypersensitivity reactions: Stop the infusion. Discontinue all protocol treatment and notify the Principal investigator or Medical Monitor.

Infusion reactions

- For grade 1 or 2 cetuximab infusion reactions: Stop the infusion until symptoms resolve, then restart cetuximab at a 50% lower rate of infusion. All subsequent doses should be administered at the lower infusion rate.
- For ≥ grade 3 cetuximab infusion reactions: Discontinue cetuximab permanently.

Other non-hematologic toxicities

- For all other ≥ grade 3 non-hematologic toxicities not described above, hold all protocol treatment and monitor toxicity at least weekly. If toxicity resolves to ≤ grade 1 or baseline within 4 weeks, treatment may be resumed with cetuximab at one lower dose level.

Dose Modification for Obese Patients

- There is no clearly documented adverse impact of treatment of obese patients when

dosing is performed according to actual body weight. Therefore, all dosing is to be determined solely by the patient's actual weight without any modification. This will eliminate the risk of calculation error and the possible introduction of variability in dose administration. Failure to use actual body weight in the calculation of drug dosages will be considered a major protocol deviation.

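### Section 6.5 gives two conflicting instructions, reduce and discontinue, for a grade 3 nail disorder that has not improved after a full 3-week hold

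*Combined protocol and SAP*

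**What the plan says.** The rule is the nail-disorder bullet of Section 6.5, a single sentence. Its first part permits a hold and attaches a reduction to lack of improvement: "For grade 3 nail disorders, cetuximab may be skipped for up to 3 weeks and if no improvement, reduce dose", to 400 mg/m² for the first occurrence, 300 mg/m² for the second and 250 mg/m² for the third. Its last part says to "discontinue cetuximab if there is no improvement after 3 weeks".

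Other text that bears on it:

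- **Table 2 (grade 3 rash, same section).** Each of the first four occurrences starts with "Skip infusion 1-2 weeks" and then has one row for improvement and another for no improvement.
- **Closing text under Table 2.** "Discontinue cetuximab if doses are skipped for more than 4 consecutive weeks".
- **Section 6.3.** "If a toxicity-related dose delay lasts for > 28 days, treatment will be discontinued permanently". The section also says that a reduction should be considered when treatment resumes.
- **Section 6.4.** After an interruption for related toxicity the drug may have to be restarted at a lower level. For when and how, it points back to the dose modification recommendations.
- **Section 6.5, other non-hematologic toxicities.** A general rule for grade 3 or worse events, limited to toxicities that the section has not already described.
- **Section 6.1.** "Cetuximab will be administered every 2 weeks (14 days"; cetuximab is the only study drug.

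**The concern.** A dose-modification rule should map each clinical state to one action. Here a single state, no improvement at the end of the permitted hold, maps to two actions that exclude each other: continue at a lower dose, or stop. The opposite state, improvement, has no action of its own in the sentence.

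The trial has two sites and one drug. If the sites read the sentence differently, a patient at one site stops all study treatment while a comparable patient at the other continues. Safety management and exposure would then depend on the site. Section 10.5 defines any noncompliance with protocol requirements as a deviation that needs corrective action and reporting, so either choice could be logged as one, because either departs from half of the sentence.

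The conflicting state is foreseeable. Section 3.2.4 says that the nail disorder can last up to 3 months after cetuximab is stopped. Persistence is not the same as absence of improvement, but a nail disorder that has not improved at 3 weeks would not be surprising.

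**Working it through.** The point is one of logic, and there is no planned figure to reproduce. The check lists every state that the nail rule can meet, reads off the action, and then asks whether other text settles the doubtful cases.

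**Step 1: states and actions in the nail sentence**

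| State after the hold | Reduction clause | Discontinuation clause | Result |
|---|---|---|---|
| Hold shorter than 3 weeks, no improvement | applies | not met | reduce only |
| Full 3-week hold, no improvement | applies | applies | two conflicting actions |
| Improvement at any time | not met | not met | no action in the sentence |

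The conflict sits in one row. The hold is optional and of variable length, which is why the first row has a single answer.

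**Step 2: does other text resolve the second row?**

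- The limits in Section 6.3 (more than 28 days) and Section 6.5 (more than 4 consecutive weeks) do not. Three weeks is 3 × 7 = 21 days, which is inside 28 days, so neither limit is reached.
- Section 6.4 refers back to Section 6.5.
- The general rule for other non-hematologic toxicities excludes those already described, and nail disorders are described.
- Table 2 governs rash only.

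**Step 3: comparison with the rash table.** For grade 3 rash, the second occurrence leads to "Reduce to 400mg/m ²" on improvement and to discontinuation on no improvement. Each outcome has one action. The nail sentence attaches both reduction and discontinuation to no improvement.

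**Step 4: the occurrence steps.** If discontinuation governed every full 3-week hold without improvement, the reduction steps could be reached only through shorter holds. If reduction governed, the discontinuation clause would need a condition that the sentence does not give, such as a particular occurrence or a later time point. A second or third occurrence also suggests that the earlier one had improved, yet the steps are triggered only by lack of improvement. With infusions every 14 days, day 21 falls between two scheduled doses (days 14 and 28, counted from the first skipped infusion), so the visit at which the outcome is judged is also open.

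**Step 5: how many patients?** Section 3.2.4 gives nail disorders of any grade in 6.4% of single-agent patients. For 21 to 25 patients this is 0.064 × 21 = 1.3 to 0.064 × 25 = 1.6 expected cases of any grade. The section also gives about 10% after more than 6 infusions, and 0.10 × 25 = 2.5, but that figure does not carry over:

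- It comes from weekly dosing. Here the seventh infusion falls at week 6 × 2 = 12, about 2.8 months.
- It applies only to patients still on treatment by then. Under the exponential model of Section 9.1, the share progression-free at 2.8 months is 0.5^(2.8/1.7) = 32% with a median of 1.7 months and 0.5^(2.8/4) = 62% with a median of 4 months. Treatment stops at progression.

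Neither rate is a grade 3 rate, and the documents give none. For scale only, one patient is 1/21 = 4.8% of the planned evaluable set.

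**The case against.** The strongest reply is that the rule is workable in practice. The hold is optional and may be short, and a short hold without improvement leads only to reduction. A clinician could take discontinuation as the last step after the third occurrence, or count the second 3 weeks from the reduction. Sections 6.3 and 6.4 already foresee that treatment resumes after an interruption, possibly at a lower dose, so the improvement case is not wholly uncovered. The toxicity is uncommon.

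Much of this stands, and it limits the point. It does not remove the conflict, because neither rescuing reading is written down and the two lead to different care for the same patient. Sections 6.3 and 6.4 leave open the dose at resumption, and they say nothing on which action follows lack of improvement.

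A reader might infer more than the documents support:

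- **That the rule cannot be followed at all.** It conflicts only after a full 3-week hold without improvement.
- **That it contradicts the 28-day and 4-week limits.** It does not; 3 weeks lies within both.
- **That the rash table shows which nail clause is a slip.** Table 2 is for another toxicity and settles nothing for this one.
- **That PFS is biased.** Stopping for toxicity is not a PFS event in Sections 2.1 or 9.3. Under Section 7.3.1, assessments continue until progression or subsequent therapy. An effect could arise only through lost exposure or through earlier new anti-cancer therapy, which does count as an event. The documents do not allow it to be sized.
- **That about two patients will meet the rule.** That count would use any-grade rates as if they were grade 3.

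**Conclusion.** The point holds in a narrow form. For a grade 3 nail disorder held the full 3 weeks without improvement, Section 6.5 orders both reduction and discontinuation, and nothing elsewhere says which applies. The nail sentence also lacks an action on improvement, a gap that Sections 6.3 and 6.4 fill only in part. This is an inconsistency within a stated safety rule, not a fault in the trial design.

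The number of patients affected is unknown, probably small and possibly zero. The judgement that it is small rests on the any-grade figures in Section 3.2.4 and on the assumption that grade 3 cases are only a part of them. No effect on PFS is claimed. The reason to act is that two sites could handle the same toxicity of the only study drug in opposite ways, and that the correction is cheap.

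**What to change.** The sponsor's clinicians should reconcile the two clauses of the nail-disorder bullet in Section 6.5. The revised text should state one action for improvement and one for no improvement at each occurrence, and say when the outcome is judged. A layout like that of Table 2 would serve; this concerns format only, and the actions are for the clinicians to decide. The revised rule should be read together with Sections 6.3 and 6.4 so that resumption after a hold is described in the same way throughout.

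The cost is a short amendment with IRB approval under Section 10.4 and a notice to both sites. No change to sample size, data collection or analysis is needed.
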